9.3 Part B Analysis

For the Part B endpoints other than those relating to relapse, rebound and duration of effects, a principal strata estimand will be used including all participants in the Part B population with all data included regardless of other intercurrent events.

These endpoints will be summarised at each visit in Parts A and B. Mean (+/- SD) values over time will also be plotted in a figure.

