- k Skin plaque biopsies (ie, a 4 mm punch biopsy, performed pre-dose by suitably trained study personnel and processed as per laboratory manual) are to be performed after all other assessments have been completed at the end of Visits 2 and 10.
- l Digital photographs should be taken of up to 6 lesion sites that have a lesion area ideally greater than 2 cm by 2 cm at baseline. The same locations photographed at baseline should be followed throughout the study for each participant.
- m Stool samples are to be collected within the 48 hours preceding each visit of stool sample collection.
- n Investigator rating scales. Participants will be asked to withhold all emollients or moisturizers on the day of these study visits until all study assessments are completed.
- o Inclusion criterion #4 (mild to moderate plaque psoriasis with plaque covering BSA of $\ge 3\%$ and $\le 10\%$, PASI score of ≥ 6 and ≤ 15 , and PGA score of 2 or 3) should be reconfirmed at the baseline visit prior to randomization.
- p Participant-reported assessments.
- q Study staff will review the dosing diaries with participants at each visit when diaries are collected. Diaries will be reviewed for completeness and accuracy, and participants will be coached as needed on compliance with the protocol.

Table 6-2 Schedule of Post-Treatment Follow-Up Assessments – Part B

Procedure	Post-Treatment Follow-Up – Part B ^a			Early Withdrawal Visit ^a
Visit number	12^b	13^b	14^c	
Months (after the End of Treatment)	2	3	6	
Weeks	24	28	40	
Day	169	197	218	–
Visit window (days)	162-176	190-204	204-232	–
BSA involvement (%), PGA, PASI ^d	X	X	X	X
LSS, mNAPSI ^d	X	X	X	X
PSI, DLQI ^e	X	X	X	X
Concomitant medication review	X	X	X	X

^a Participants who withdraw from the study during Part B should complete the final assessments at the Early Withdrawal Visit (where relevant and when possible, this should be arranged within 72 hours of the start of a new psoriasis treatment).

^b All participants will attend Visits 12 and 13, unless they are considered a ‘treatment failure’ or meet the criteria for rebound.

^c Only participants who are classified as responders at Week 16 (Visit 10) and have not relapsed at Week 28 (Visit 13) will be eligible for Visit 14 (Week 40).

^d Investigator rating scales. Participants will be asked to withhold all emollients or moisturizers on the day of these study visits until all study assessments are completed.

^e Participant-reported assessments.

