7.1.6 Part B Population

The Part B population will consist of all participants who entered Part B of the study.

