15.5 Part B Outputs

15.5.1 Tables

Number	Title	Population	Programming notes
14.4.1.1	Summary of Disposition in Part B	Part B	
14.4.1.2	Summary of Attendance at Each Visit in Part B	Part B	
14.4.1.3	Summary of Missed Visits Due to COVID-19 in Part B	Part B	
14.4.1.4	Summary of Populations	Part B	
14.4.1.5	Summary of Demography	Part B	
14.4.1.6	Summary of Baseline Disease Characteristics	Part B	
14.4.1.7	Summary of Concomitant Medications Used in Part B	Part B	
14.4.2.1	Summary of Percentage Change from Baseline in PASI Score	Part B	
14.4.2.2	Summary of Change from Baseline in PASI Score	Part B	
14.4.2.3	Summary of Percentage Change from Baseline in PGA*BSA	Part B	
14.4.2.4	Summary of Change from Baseline in PGA*BSA	Part B	
14.4.2.5	Summary of Percentage Change from Baseline in LSS	Part B	
14.4.2.6	Summary of Change from Baseline in LSS	Part B	
14.4.2.7.1	Summary of Percentage Change from Baseline in DLQI Score - Main Analysis	Part B	
14.4.2.7.2	Summary of Percentage Change from Baseline in DLQI Score – Sensitivity Analysis	Part B	
14.4.2.8.1	Summary of Change from Baseline in DLQI Score - Main Analysis	Part B	
14.4.2.8.2	Summary of Change from Baseline in DLQI Score - Sensitivity Analysis	Part B	
14.4.2.9	Summary of Percentage Change from Baseline in mNAPSI Total Score for Participants with Psoriatic Nail Involvement at Baseline	Part B	
14.4.2.10	Summary of Change from Baseline in mNAPSI Total Score for Participants with Psoriatic Nail Involvement at Baseline	Part B	
14.4.2.11	Summary of Percentage Change from Baseline in PSI Total Score	Part B	

Number	Title	Population	Programming notes
14.4.2.12	Summary of Change from Baseline in PSI Total Score	Part B	
14.4.2.13	Summary of Percentage Change from Baseline in PSI Itch Score	Part B	
14.4.2.14	Summary of Change from Baseline in PSI Itch Score	Part B	
14.4.2.15	Cumulative Incidence of Partial Relapse	Week 16 Responders	
14.2.2.16	Cumulative Incidence of Relapse	Week 16 Responders	
14.4.2.17	Cumulative Incidence of Rebound	miITT	
14.4.2.18	Summary of Duration of Remission	miITT	
14.2.2.20	Summary of Duration of Treatment Success	miITT	
14.4.2.21	Summary of Duration of Therapeutic Effect	miITT	
14.4.3.1	Overview of Related TEAEs Starting in Part B	Part B	
14.4.3.2	Summary of Related TEAEs by System Organ Class and Preferred Term Starting in Part B	Part B	

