15.5.2 Figures

Number	Title	Population	Programming notes
14.4.2.1	Mean (+/-SD) Percentage Change in PASI Score Over Time	Part B	
14.4.2.2	Mean (+/-SD) Change in PASI Score Over Time	Part B	
14.4.2.3	Mean (+/-SD) Percentage Change in PGA*BSA Over Time	Part B	
14.4.2.4	Mean (+/-SD) Change in PGA*BSA Over Time	Part B	
14.4.2.5	Mean (+/-SD) Percentage Change in LSS Over Time	Part B	
14.4.2.6	Mean (+/-SD) Change in LSS Over Time	Part B	
14.4.2.7.1	Mean (+/-SD) Percentage Change in DLQI Score Over Time – Main Analysis	Part B	
14.4.2.7.2	Mean (+/-SD) Percentage Change in DLQI Score Over Time – Sensitivity Analysis	Part B	

Number	Title	Population	Programming notes
14.2.2.8.1	Mean (+/-SD) Change in DLQI Score Over Time – Main Analysis	Part B	
14.2.2.8.2	Mean (+/-SD) Change in DLQI Score Over Time – Sensitivity Analysis	Part B	
14.4.2.9	Mean (+/-SD) Percentage Change in mNAPSI Total Score Over Time for Participants with Psoriatic Nail Involvement at Baseline	Part B	
14.4.2.10	Mean (+/-SD) Change in mNAPSI Total Score Over Time for Participants with Psoriatic Nail Involvement at Baseline	Part B	
14.4.2.11	Mean (+/-SD) Percentage Change in PSI Total Score Over Time	Part B	
14.4.2.12	Mean (+/-SD) Change in PSI Total Score Over Time	Part B	
14.4.2.13	Mean (+/-SD) Percentage Change in PSI Itch Score Over Time	Part B	
14.4.2.14	Mean (+/-SD) Change in PSI Itch Score Over Time	Part B	
14.4.2.15	Cumulative Incidence (+/- 95% CI) of Partial Relapse	Week 16 Responders	
14.4.2.16	Cumulative Incidence (+/- 95% CI) of Relapse	Week 16 Responders	
14.4.2.17	Cumulative Incidence (+/- 95% CI) of Rebound	miITT	

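### Part B by-visit means run to Week 40 in the whole Part B population, but only unrelapsed Week 16 responders are scheduled for Week 40, so the last segment can show improvement that is only selection

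*SAP*

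**What the plan says.** SAP 9.3 covers the Part B endpoints other than relapse, rebound and duration. It says that "a principal strata estimand will be used including all participants in the Part B population with all data included regardless of other intercurrent events". It continues: "These endpoints will be summarised at each visit in Parts A and B", and "Mean (+/- SD) values over time will also be plotted in a figure". SAP 7.1.6 defines the population broadly: "The Part B population will consist of all participants who entered Part B of the study".

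The outputs follow this. Table 14.4.2.1 ("Summary of Percentage Change from Baseline in PASI Score") and Figure 14.4.2.1 ("Mean (+/-SD) Percentage Change in PASI Score Over Time") are both on the Part B population. The same form is used up to number 14.4.2.14 for absolute PASI change, PGA*BSA, LSS, DLQI, mNAPSI and PSI. SAP 7.3 allows no imputation beyond item-level scoring rules, so each mean uses whoever attended.

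Attendance depends on outcome. Protocol Table 6-2, footnote b: "All participants will attend Visits 12 and 13, unless they are considered a ‘treatment failure’ or meet the criteria for rebound". Footnote c, for Week 40: "Only participants who are classified as responders at Week 16 (Visit 10) and have not relapsed at Week 28 (Visit 13) will be eligible". SAP 5.1 gives the same Week 40 rule in terms of complete relapse. Under SAP 5.3.3.2, response is PASI-50 at Week 16, and relapse is PASI back to baseline or above, or a new psoriasis treatment.

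**The concern.** Each curve joins a near-complete group at Week 28 to a group at Week 40 picked because its PASI was low at Week 16 and stayed below baseline. SAP 7.3, 7.7, 8, 9.3 and 15.5 neither stop the curve at Week 28 nor hold the participants constant. The principal-stratum label does not help: the stratum named is everyone who entered Part B, and its non-responders are not scheduled for Week 40.

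Part B is meant to show how long response lasts and whether disease rebounds. A reader of these figures could take the last segment as benefit deepening between 3 and 6 months off drug, in the placebo arm as well, or as drug and placebo converging. Either impression could come from the visit rule alone.

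**Working it through.** **Inputs from the documents.** SD of percent change in PASI 25 and difference of interest 20 points (SAP 6); 42 evaluable per active dose and 3 x 21 = 63 pooled placebo (SAP 6); attendance rules as above.

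**Assumed, not in the documents.** True mean change of -30 (active) and -10 (placebo), constant from Week 16 to Week 40; normal distribution; two-sided 5% for power; and the between-visit correlation, taken either as constant or as decaying by a fixed factor per 4 weeks (AR(1)). Withdrawals for new treatment are not modelled.

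**1. The plan's own figures.** Pooled: SE = 25 x sqrt(1/42 + 1/63) = 4.98; 20/4.98 - 1.96 = 2.06; power 98.0%. Within cohort: SE = 25 x sqrt(1/42 + 1/21) = 6.68; 20/6.68 - 1.96 = 1.03; power 84.9%. These agree with the stated >95% and >80%, so the inputs are being read as the plan reads them.

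**2. Direction and rough size by hand.** For a normal variable, the mean at Week 16 among responders is mu - 25 x phi(z)/Phi(z), with z = (-50 - mu)/25.
- Active: z = -0.8, responders 21.2%, mean -30 - 25 x 0.2897/0.2119 = -64.2.
- Placebo: z = -1.6, responders 5.5%, mean -10 - 25 x 0.1109/0.0548 = -60.6.

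If r is the correlation between Weeks 16 and 40, their Week 40 mean is mu + r x (responder mean - mu). At r = 0.7 this is -30 - 0.7 x 34.2 = -53.9 on active and -10 - 0.7 x 50.6 = -45.4 on placebo. Any positive r puts the Week 40 mean below mu, and the pull is larger on placebo.

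**3. Simulation with the full attendance rules.** Weeks 24 and 28 drop anyone at +25% or worse at an earlier follow-up visit. Week 40 keeps change <= -50% at Week 16 and < 0 at Weeks 20, 24 and 28.

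| Correlation | Active, Wk 28 to 40 | Placebo, Wk 28 to 40 | Steps | Gap plotted at Wk 40 (true 20) |
|---|---|---|---|---|
| AR(1) 0.7 per 4 weeks | -30.9 to -34.9 | -13.7 to -18.0 | 4.0, 4.3 | 16.9 |
| AR(1) 0.8 | -31.0 to -39.4 | -14.1 to -24.5 | 8.4, 10.4 | 14.9 |
| AR(1) 0.9 | -31.1 to -48.1 | -14.5 to -37.1 | 17.0, 22.6 | 11.0 |
| Constant 0.7 | -31.0 to -54.0 | -14.3 to -45.9 | 23.0, 31.6 | 8.1 |
| Constant 0.85 | -31.1 to -58.9 | -14.7 to -53.0 | 27.8, 38.3 | 5.9 |

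The plotted gap is already about 16 to 17 at Week 28, because rebounders have left. At AR(1) 0.7 there is therefore almost no further compression at Week 40. At AR(1) 0.5 the 12-week correlation is only 0.5^3 = 0.125, and a further run gives steps within 1 point of zero in either direction.

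**4. Numbers contributing.** At constant 0.7, about 21% of active (0.211 x 42 = 8.9) and 5% of placebo (0.053 x 63 = 3.3) reach Week 40.

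**5. The curve can run against its own members.** At AR(1) 0.9, the active participants seen at Week 40 go from -55.0 at Week 28 to -48.1, a worsening. The plotted curve goes from -31.1 to -48.1, an improvement.

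**6. Same people at both visits.** At constant 0.7 with the same means, the Week 40 attendees go from -54.1 to -54.0 (active) and -46.0 to -45.9 (placebo). The step disappears.

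**The case against.** The size rests on a correlation that the documents do not give. Constant correlation is the unfavourable case, because it lets Week 16 predict Week 40 as well as it predicts Week 20. Decaying correlation is at least as plausible and gives much smaller steps. Any real loss of effect off drug would also offset the step. This stands: a reader might infer a marked jump in every arm, or a gap shrunk to 6 to 8 points, but those hold only for the high, constant correlations.

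A reader might also infer that these are Part B's main curves and that its durability conclusions fail with them. The documents do not support that. The Part B objectives are relapse and rebound, plus exploratory durations, and SAP 4.2 lists no continuous score after Week 16 as an endpoint. Relapse is analysed in the Week 16 responders population, and SAP 9.5.6 counts a relapsed participant as relapsed at every later visit, so missing Week 40 hides no one.

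There are safeguards. Section 8 of the SAP reports n with each mean, Table 14.4.1.2 shows attendance, and SAP 5.1 states the Week 40 rule. Section 11 gives no mean when n < 3 and no SD when n = 3. With a binomial of 63 at 5%, pooled placebo has n < 3 with probability about 0.38 and n <= 3 about 0.61, so a placebo mean at Week 40 may often be absent from the table. But n does not tell the reader that attendees were selected on PASI, and the SAP does not ask for n on the figures.

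Finally, a responder-only display has its own artefact. Under the no-change model at correlation 0.7, responders move from -64.1 at Week 16 to -53.8 at Week 20 on active and from -60.6 to -45.4 on placebo. These false losses of about 10 and 15 points flatter the drug. The fix has to say so.

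**Conclusion.** The point holds as a fault in descriptive displays. Followed as written, the plan joins two differently selected groups on one line, and that needs no assumption beyond the documents. Selection pulls the Week 40 mean towards improvement in every arm at any positive correlation with Week 16. It shows as a false Week 28 to Week 40 step unless correlation has nearly died out over those 12 weeks.

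Under the stated assumptions the step is about 4 points (AR(1) 0.7), 8 to 10 (AR(1) 0.8), 17 to 23 (AR(1) 0.9) or 23 to 38 (constant 0.7 to 0.85), and the 20-point gap is plotted as about 17 down to 6. The structure is certain; the size is not. The relapse, rebound and duration endpoints are not built from these means and are not affected.

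**What to change.** In SAP 9.3 and outputs 14.4.2.1 to 14.4.2.14, end the Part B-population by-visit means and curves at Week 28. The small shift from rebounders and treatment failures leaving before Week 28 remains and can be footnoted.

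Show Week 40 only in a separate display, labelled as the Week 16 responders population. Print n and the cumulative number relapsed at each visit. Do not carry values forward: that would depart from SAP 7.3 and, in the simulation, changes the means by at most 0.6 points at correlation 0.7. Add a note that selection on Week 16 response makes the Week 16 to Week 20 change partly regression to the mean.

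The cost is SAP wording and one extra display per endpoint. No new data, visits or participants are needed.

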9.4 Primary Efficacy Analysis

9.4.1 Primary Efficacy Estimand

The primary efficacy estimand will be the effect of EDP1815 compared to placebo on the percentage change from baseline to Week 16 in PASI score. The population summary measure of interest will be the difference in mean percentage change from baseline in PASI score at Week 16.

Intercurrent events will be accounted for in the following manner:

Table 3 Intercurrent Event Strategies for the Primary Estimand

Intercurrent event	Strategy to account for intercurrent event
Protocol deviation with potential to impact efficacy	Treatment policy PASI scores will be used as collected regardless of whether a protocol deviation occurred
Treatment discontinuation for any reason *	While on treatment PASI scores collected more than 4 days after treatment discontinuation will be considered as missing for all timepoints up to Week 16. For the Week 20/follow-up visit, PASI scores will be considered as missing for subjects who did not complete treatment up to Week 16.

* This includes participants who completed the 16-week treatment period but have their Week 16 visit more than 4 days after the end of treatment.

9.4.2 Supportive Estimands for the Primary Endpoint

For the primary analysis, three supportive estimands will be considered in order to assess the impact of intercurrent events.

Table 4 Supportive Estimands for the Primary Endpoint

Estimand	Purpose	Population	Intercurrent Event Strategy
Primary Supportive Estimand 1	Assess the impact of protocol deviations which may impact efficacy	PP	Protocol deviation with potential to impact efficacy While on treatment (PASI scores collected after the occurrence of the protocol deviation will be considered missing) Treatment discontinuation for any reason before Week 16 While on treatment (as per Primary estimand)

Estimand	Purpose	Population	Intercurrent Event Strategy
Primary Supportive Estimand 2	Assess the impact of treatment discontinuation for any reason	miITT	
Protocol deviation with potential to impact efficacy
 
Treatment policy (as per Primary estimand)
 
Treatment discontinuation for any reason before Week 16
 
Treatment policy (PASI scores collected more than 4 days after treatment discontinuation will be included). Note that Week 20/follow-up data will still only be included for subjects who completed treatment.

Primary Supportive Estimand 3	Assess the impact of treatment discontinuation due to requirement for alternative therapy	miITT	
Protocol deviation with potential to impact efficacy
 
Treatment policy (as per Primary estimand)
 
Treatment discontinuation due to requirement for alternative therapy before Week 16
 
Composite (highest recorded on-treatment PASI score carried forward to all scheduled visits after treatment discontinuation)
 
Treatment discontinuation for any other reason before Week 16
 
While on treatment (as per Primary estimand)

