7.1 Estimands and Intercurrent Events

7.1.1 Primary Efficacy Estimand

The primary estimand will be the effect of EDP1815 on the percent change in PASI score from baseline to Week 16 in the mITT set of all treated participants, regardless of deviations from the protocol. Only data collected while on treatment will be used to account for the intercurrent event of treatment discontinuation (hypothetical strategy based on adherence to treatment only). The posterior mean difference between each active dose and the pooled placebo will be estimated.

Percent change from baseline in PASI score at each visit will be calculated as:

$$100 * (\text{PASI score at Visit} - \text{baseline PASI score}) / \text{baseline PASI score}.$$

A negative percentage change from baseline will indicate an improvement.

For the primary analysis, 3 supportive estimands will also be considered:

- To assess the impact of intercurrent events related to protocol deviations believed to impact efficacy, a supportive analysis will be performed where all data collected after any such identified protocol deviations will be excluded. Participants who had a protocol deviation believed to impact efficacy prior to the first dose of treatment (hypothetical strategy based on adherence to treatment and the aspects of the protocol which impact efficacy) will be completely excluded from this analysis.
- To assess the impact of treatment discontinuation for any reason, a supportive analysis will be performed in which all data collected up to the end of Week 16, including any data collected after treatment discontinuation will be included (treatment policy strategy).
- To assess the impact of treatment discontinuation due to a requirement for alternative therapy, a supportive analysis will be performed where the highest PASI score recorded prior to treatment discontinuation will be applied to all expected visits after treatment discontinuation up to Week 16.

The primary analysis will be performed using a Bayesian MMRM as fully described in Section 7.6.1. Data from visits prior to Week 16 will be included in the model and missing data will not be explicitly imputed.

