5.3.1.2 Baseline

The last non-missing value collected before first study dose will be taken as the baseline measurement for all parameters. If data is collected on Day 1 without an associated time being provided, it will be assumed to be pre-dose. Efficacy data collected using the electronic clinical outcome assessment (eCOA) device on the same day as the first dose of study medication will also be assumed to be pre-dose data and can be used for the baseline assessment, regardless of whether the time indicates if it was before or after the time of first dose.

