7.1.2 Modified Intention to Treat Population

The modified intention to treat (mITT) population will consist of all participants who were randomised to treatment and who received at least one dose of study treatment. Participants who withdraw from the study before the end of Week 4 and are replaced will be included in this analysis set.

All analyses using the mITT population will group participants according to randomised treatment.

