9.4.3 Main Analytical Approach

Percentage change from baseline in PASI score at each visit will be summarised. Mean (+/- SD) percentage change from Baseline over time will be plotted in a figure. Also, waterfall plots will be created to show the ranked individual percentage change from Baseline at Week 16.

The primary analysis will be performed using a Bayesian mixed model for repeated measures (MMRM). The model will include parameters for treatment*visit and baseline PASI score*visit interactions and will not include an intercept.

Treatment will consist of 4 levels (all placebo, EDP1815 1 capsule, EDP1815 4 capsules and EDP1815 10 capsules) if the placebo pooling strategy is considered appropriate or 6 levels (Placebo 1 capsule, Placebo 4 capsules, Placebo 10 capsules, EDP1815 1 capsule, EDP1815 4 capsules, and EDP1815 10

capsules) if the placebo pooling strategy is not considered appropriate. Visit will consist of 7 levels (Weeks 1, 2, 4, 8, 12,16 and 20).

As described in [Section 9.2](#) additional covariates for baseline factors will be assessed using this model for inclusion in all efficacy models.

The priors for all parameters in the model will be non-informative and follow a normal distribution with mean 0 and SD 1000. The prior for the variance-covariance matrix will follow an inverted Wishart distribution with degrees of freedom equal to the number of visits and an identity scale matrix. The choice of Wishart distribution is based on it being the conjugate prior of the inverse-covariance matrix of a multivariate-normal random vector.

The model will be blocked so that the MCMC procedure samples from the treatment*visit parameters first, then the baseline*visit parameters, then any additional fitted covariates and finally the variance-covariance matrix.

100,000 MCMC samples will be generated with a thin of 20 to leave 5000 retained samples after a burn-in of 10,000 samples. The number of samples or thin may be increased to reduce the ratio of the Monte Carlo standard error (MCSE) to the posterior SD, as deemed necessary.

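### SAP Supportive Estimand 3 leaves baseline out of the worst PASI it carries forward, so a participant who stops for alternative therapy can be imputed as improved

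*SAP*

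**What the plan says.** The stated purpose of Supportive Estimand 3 in SAP 9.4.2, Table 4, is to "Assess the impact of treatment discontinuation due to requirement for alternative therapy". Its rule is "Composite (highest recorded on-treatment PASI score carried forward to all scheduled visits after treatment discontinuation".

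Protocol 7.1.1, repeated in the synopsis, describes the same supportive analysis differently: the "highest PASI score recorded prior to treatment discontinuation will be applied to all expected visits after treatment discontinuation up to Week 16".

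Three other definitions bear on this:

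- SAP 5.3.1.2: "The last non-missing value collected before first study dose will be taken as the baseline measurement for all parameters". Efficacy data entered on the electronic device on the day of first dose also count as pre-dose, whatever the clock time.
- SAP 9.4.1, Table 3, sets the end of the on-treatment window: "PASI scores collected more than 4 days after treatment discontinuation will be considered as missing for all timepoints up to Week 16". The SAP gives no other definition of on-treatment.
- SAP 7.1.2: the mITT population is everyone "randomised to treatment and who received at least one dose of study treatment". No post-baseline PASI is required.

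SAP Table 8 lists four departures from the protocol. This is not one of them.

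**The concern.** A composite strategy is meant to build the intercurrent event into the outcome as an unfavourable result. Treatment failure here is defined by starting another therapy (protocol 4.2, SAP 5.1), not by a PASI threshold. A participant can therefore fail while every post-baseline score is somewhat below baseline. Under the SAP wording that participant carries forward a negative percent change, and on this endpoint "A negative percentage change from baseline will indicate an improvement". A participant with no on-treatment PASI has nothing to carry forward. SAP 7.3 then leaves the value missing for the mixed model to handle.

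Among the SAP's estimands for the primary endpoint, this is the only one meant to count need for alternative therapy against the participant. The primary estimand and Supportive Estimand 1 set later scores to missing, and Supportive Estimand 2 uses them as collected. SAP 9.5.3.2 handles the same event for PASI-50 by scoring non-response whatever the earlier scores, so the SAP's two composite rules do not match. SAP 9.4.4 also repeats the dose-response analysis when a supportive result differs substantially from the primary one. A softened imputation could mask such a difference.

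**Working it through.** **Scale of the trial.** SAP section 6 gives a difference of 20, SD 25, and 42 active and 21 placebo completers per cohort (63 pooled placebo). A two-sided 5% level is assumed.

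- Pooled: SE = 25 × √(1/42 + 1/63) = 4.98. Power = Φ(20/4.98 − 1.96) = 98.0%. The plan says more than 95%.
- Within cohort: SE = 25 × √(1/42 + 1/21) = 6.68. Power = Φ(20/6.68 − 1.96) = 84.9%. The plan says more than 80%.

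Both figures reproduce and are not in dispute. The 4.98 serves below as a yardstick.

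**Participant level.** Percent change = 100 × (imputed − baseline)/baseline. The cases are illustrative, with baselines inside the eligible range of 6 to 15.

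| Baseline | On-treatment PASI | SAP rule | Maximum including baseline |
|---|---|---|---|
| 10 | 8, 7 | 8, −20.0% | 10, 0% |
| 10 | 8, 8.5, 7.5 | 8.5, −15.0% | 10, 0% |
| 15 | 14, 13 | 14, −6.7% | 15, 0% |
| 10 | 9, 11 | 11, +10.0% | 11, +10.0% |
| 12 | none | no value | 12, 0% |

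The rules differ only when no on-treatment score reaches baseline. With baseline included, the result cannot fall below 0.

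**The no-score case.** The first post-baseline PASI is at Week 1 (window Days 5 to 11). A score taken on Day 8 still counts for someone who stopped on Day 4, since 8 − 4 = 4 days is not more than 4. Only those who stop in roughly the first days, or who miss Week 1 and stop before a later score, have nothing to carry. Protocol Table 6-1 asks for a visit within 72 hours of a new psoriasis treatment, but SAP 7.7 keeps unscheduled visits and early-withdrawal follow-up data out of by-visit analyses. That visit is not a clear fallback.

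**Arm level.** The documents give no rate of discontinuation for alternative therapy, so these counts are assumptions. Each such participant is credited −20 instead of 0.

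- 8 of 75 placebo: 8 × (−20)/75 = −2.13. 2 of 50 active: 2 × (−20)/50 = −0.80. Active minus placebo changes by −0.80 − (−2.13) = +1.33, toward the null if active is better. 1.33/4.98 = 0.27 of a standard error.
- Other direction, 3 of 75 placebo and 5 of 50 active: −0.80 and −2.00. The difference changes by −1.20, in favour of active.

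**Range by simulation.** Assumptions, none from the documents except the SD: normal percent changes with SD 25 at each visit, between-visit correlation 0.5 or 0.8, 1 to 5 on-treatment visits, and a mean on-treatment change of 0 to −20 among these discontinuers. Between 17% and 79% of them are scored as improved. Leaving out baseline lowers their imputed mean by about 2 to 23 points. The arm mean moves 0.1 to 1.2 points if 5% of the arm stop for this reason, and 0.3 to 3.5 points if 15% do. The plan's ceiling for discontinuation from all causes is 15%.

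**The case against.** The strongest reply is that worst on-treatment score carried forward is already an unfavourable composite, and that someone always below baseline did improve, though not enough. The protocol never names baseline. PASI is also scored at screening, so its wording read literally would admit the screening score too: with screening 14, baseline 10 and no on-treatment score, the imputed change would be +40%. Restricting to on-treatment scores may be a deliberate clarification. A sensitivity analysis deleted in Amendment 4 used the on-treatment maximum; that text is superseded, but it makes the intention plausible. It therefore stands that including baseline is an inference from the protocol wording, not a rule the protocol states. It does not explain why Table 8 is silent, or why a failure should score as an improvement here when the PASI-50 composite forbids it.

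Protocol 7.6.1 also plans a harsh imputation of 100% in a dose-response sensitivity analysis. That tempers the concern at protocol level, but SAP 9.4.4 contains no such imputation.

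A reader might take −20% as equal to the trial's own clinically meaningful effect. SAP section 6 defines that 20% as a difference relative to placebo. Nothing in the plan calls a −20% change within one participant clinically meaningful, and response requires PASI-50.

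**Conclusion.** The mismatch is real and worth correcting. It affects one supportive analysis in a trial with no formal hypothesis test, and the primary estimand and the power statement are untouched. That a failure can be imputed as improved, or get no composite value, follows from the text, given that on-treatment excludes a pre-dose baseline. The arm-level size is probably small: about 1.3 points, or roughly a quarter of a standard error, on assumed counts. The placebo count is 8/75 = 10.7% for a single reason, which already uses most of the 15% ceiling.

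Two stronger readings are not supported. One is that early failures in general drop out: the 4-day window confines this to a narrow group. The other is that the SAP rule favours the drug, or that correcting it makes the analysis more conservative: the shift goes either way, depending on which arm has more of these discontinuations.

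**What to change.** In Table 4, define the imputed score as the maximum of (a) the baseline PASI as defined in SAP 5.3.1.2, not the screening score when a later baseline exists, and (b) all post-baseline on-treatment PASI scores, meaning those up to 4 days after discontinuation. Apply it to scheduled visits after discontinuation up to Week 16. A participant with no on-treatment score then takes the baseline value, a 0% change. Stating the Week 16 limit also settles a second mismatch: Table 4 says all scheduled visits and the SAP model runs to Week 20, while the protocol stops at Week 16.

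If the narrower rule is intended, list and justify it in Table 8 and say what happens when no on-treatment score exists.

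The cost is one SAP sentence and one derivation line. The downside is a harsher imputation for these participants, which may move the treatment contrast in either direction.
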